11 DISSEMINIATION POLICY	
11.1 Dissemination policy	21
11.2 Authorship eligibility guidelines and any intended use of professional writers	21
12 REFERENCES	20
13. APPENDICES	22

LIST OF ABBREVIATIONS

Term	Definition		
AIC	Akaike Information Criteria		
ASD	Autistic Spectrum Disorder		
BAME	Black, Asian, and Minority Ethnic		
CBCL	Child Behaviour Checklist		
CHU-9D	Child Health Utility 9 Dimensions		
CI	Chief Investigator		
CRF	Case Report Form		
СҮР	Children and Young People		
GCP	Good Clinical Practice		
GD	Gender Dysphoria		
GI	Gender Identity		
GIDS	Gender Identity Development Service		
GDPR	General Data Protection Regulation		
GnRH	Gonadotropin Releasing Hormone		
GLM	General Linear Model		
HRA	Health Research Authority		
HS&DR	Health Service and Delivery Research		
ICF	Informed Consent Form		
IRAS	Integrated Research Application System		
ISF	Investigator Site File		
ISRCTN	International Standard Randomised Controlled Trials Number		
NMB	Net Monetary Benefit		
NHS R&D	National Health Service Research & Development		
NIHR	National Institute for Health Research		
PI	Principal Investigator		
PIS	Participant Information Sheet		
PPI	Patient Public Involvement		
QALY	Quality Adjusted Life Years		
REC	Research Ethics Committee		
SDQ	Strengths and Difficulties Questionnaire		
SDV	Source Document Verification		
SRS-2	Social Responsiveness Scale		
SOP	Standard Operating Procedure		
SSC	Study Steering Committee		
YSR	Youth Self Report		
	1		

STUDY SUMMARY

Study Title	Longitudinal Outcomes of Gender Identity in Children
Internal ref. no. (or short title)	LOGIC
Research Questions/Aims	1. What is the profile of children and young people
	(CYP) referred to GID services?
	2. What proportion of children and young people, aged
	3-13 years when their referral was accepted to these
	services experience ongoing gender dysphoria; and go
	on to have physical treatment? What are the predictors
	of such occurrences?
	3. What is the impact of a) physical treatment, b) social
	transition, and c) co-occurring autism on physical
	health, psychological wellbeing, quality of life, peer
	and family relationships, and cost to the NHS and
	other public services?
	4. What is the experience of children and young people,
	and their families over time referred to GID services?
Study Participants	Children and young people (CYP) aged 3-13 years at the time
	of referral acceptance to the UK Gender Identity
	Development Service (GIDS), and their caregivers.
Planned Size of Sample (if	We will aim to recruit a total of 638 children and young
applicable)	people to the quantitative study. A total of 40 families,
	consisting of both the children and young people attending the
	UK GID service and their caregivers, will be recruited to the
	qualitative arm of the study.
Follow up duration (if applicable)	2 years
Planned Study Period	48 months

FUNDING AND SUPPORT IN KIND

(Names and contact details of ALL organisations providing funding and/or support in kind for this study) SUPPORT GIVEN	(Names and contact details of ALL organisations providing funding and/or support	FINANCIAL AND NON FINANCIAL SUPPORT GIVEN
---	--	---

_	IHR Health Services & Delivery Research rogramme	£ 1.3 million financial support (for overall study)	

ROLE OF STUDY SPONSOR

The sponsor is responsible for confirming that the study design has integrity, the resources required for initiation are secured, all applicable regulatory approvals have been received before commencement, and that arrangements are in place for monitoring and reporting to ensure research conduct is in compliance with Good Clinical Practice (GCP) and all applicable laws and regulations. The sponsor will also confirm that there is a clear dissemination and data retention plan once the study has closed.

ROLES AND RESPONSIBILITIES OF STUDY MANAGEMENT COMMITEES/GROUPS & INDIVIDUALS/FUNDER

Study Steering Group/Funder

The Study Steering Committee (SSC) will provide overall supervision for the project on behalf of the Project Sponsor and Funder to ensure that the project is conducted to the rigorous standards set out in the Department of Health's Research Governance Framework for Health and Social Care and the Guidelines for Good Clinical Practice. It will include an independent chair, PPI representatives, and independent clinicians and academics who will meet every 4-6 months. These will report to NIHR and the sponsor as required. There will also be ongoing communication every 6-8 months with 'internal' PPI advisory groups consisting of children and young people attending the GID service and their parents.

KEY WORDS: Gender dysphoria; Gender identity; Children and Young People; Prospective cohort; Longitudinal

STUDY PROTOCOL

Longitudinal Outcomes of Gender Identity in Children (LOGIC)

1 BACKGROUND

Emerging data from several countries suggest that gender diversity in children and young people is more common than previously thought (1). This is reflected in the significant increase in referrals reported in gender clinics across a number of countries. For instance, in the UK, rates of referral rose from 97 to 2,519 yearly referrals in approximately a decade. Such rise in referrals is also accompanied with a younger age at time of referral and a rise in children accessing physical treatments (2-4).

While not all gender-diverse children and young people will experience gender dysphoria (that is, the experience of distress associated with a mismatch between the sex assigned at birth and gender identity), a proportion do. The available evidence suggests that gender dysphoria is associated with a range of negative mental and physical health difficulties, including depression, anxiety, suicidality and substance abuse (5-10). Current NHS intervention for children and young people experiencing gender dysphoria is aimed at alleviating dysphoric feelings, improving psychological wellbeing and supporting young people and their families to make informed decisions about treatment and the meaning of gender identity within their lives and contexts (11). However, the evidence base on which the current treatment protocols are based is widely acknowledged to be both limited and shifting (12). To date, no information exists to help us clinically predict individual gender and psychosexual developmental pathways (12). It is difficult to estimate what proportion of younger pre and peripubertal children and young people referred to NHS services will later access physical treatment to suppress puberty. We are also currently unaware of the factors that predict the likelihood of receiving such treatment from the NHS, and the physical and psychological impact of such treatment (13).

Internationally, the need for longitudinal evidence to inform the care of gender diverse children and young people is well established in the literature (12). In light of this dearth of research, the proposed study aims to investigate the mental and physical health outcomes of children and young people referred to the UK's Gender Identity Development Service. It will compare the outcomes of those who pursue physical intervention to those who do not, and explore the impact of factors such as co-occurring Autism Spectrum Disorder (ASD) and a decision to socially transition (i.e. change name, pronouns, clothing etc. to better reflect their gender identity), on such outcomes over time.

Furthermore, it will describe the experiences of those referred onto the service and their families, in order for us to better understand their changing perceptions of gender identity within the context of their lives, the factors that may influence such changes, and how their experiences of help seeking, health services and therapies can be improved.

2 RATIONALE

Very little is known overall about the profile of children and younger adolescents referred to Gender Identity Development (GID) services. At present, we are unaware, both in the UK and internationally, of the outcomes and likely trajectories of children and young people presenting to these services.

A key question for the NHS pertains to the proportion of gender diverse children and young people presenting to services who later go on to receive treatment with hormone blockers, and which factors predict this. Additionally, major knowledge gaps currently exist in relation to the immediate and long-term impact of a) physical treatment commencing in early puberty b) early social transition c) and co-occurring Autistic Spectrum Disorder (ASD).

This study will characterise the entire cohort of children and younger adolescents aged between 3 and 13 years at the time of referral to a GID service. It will help us develop a greater understanding of the individual differences in those referred to the service. The findings generated from this research will enable services to provide better, more individualised care, which will provide immediate benefits to patients and their families.

3 RESEARCH QUESTION/AIM(S)

- 1. What is the profile of children and young people referred to GID services?
- 2. What proportion of children and young people, aged 3-13 years when their referral was accepted to these services experience ongoing gender dysphoria, and go on to have physical treatment? What are the predictors of such occurrences?
- 3. What is the impact of a) physical treatment b) social transition c) co-occurring autism on, physical health, psychological wellbeing, quality of life, peer and family relationships and cost to the NHS and other public services?
- 4. What is the experience of children and young people, and their families after they are referred to GID services?

3.1 Objectives

Our objective is to undertake a prospective longitudinal study of children and young people aged 3-13 years at the time of referral acceptance to the UK's GID service, consisting of both:

- 1. quantitative assessments at baseline and at yearly follow-up over two years;
- 2. qualitative interviews with both those referred and their caregivers, at baseline and at yearly follow-up over two years in a sub-sample of 40

3.2 Outcome

This research will generate important new insights about a population of children and young people who experience significant distress about their gender identity and are referred to a GID service for support and/or long-term intervention. Making as accurate an assessment as possible at a younger age has profound implications for the psychological and physical wellbeing of the individual but also for the cost to the NHS and public funds. The study will seek to identify the factors that influence this group's mental health, behavioural and emotional functioning, and quality of life. It will identify the factors that influence whether a child or young person chooses physical/endocrine treatment and compare the mental health, wellbeing and physical health outcomes for those in receipt of endocrine treatment with those of a similar age/pubertal stage not receiving such treatment. It will also explore the impact of factors such as a) co-occurring ASD, and b) a decision to socially transition, on outcomes over time.

Health economic data will be generated regarding the costs and consequences of a range of service, intervention and children and young people/family characteristics. The qualitative component of the longitudinal study will complement the quantitative elements by providing in-depth data on experience of gender diversity issues and services and how these change over time from the perspective of children and young people and their families. This will include those who do not progress through GIDs services as well as those who do.

The data generated will be used as material to develop multi-media resources to inform children and young people and their families about the differing narratives and trajectories of this group. These resources will be developed in consultation with key stakeholders and will aim to convey, in a child and family centred way, the 'human stories behind the figures'. These multi-media resources will also assist in the education of NHS commissioners and clinicians, schools and other relevant service providers, and thereby help to enhance therapies and support for children and young people and their families.

LOGIC's key findings will be disseminated through diverse and innovative methods that target policy makers, service planners, accreditation bodies, clinicians and service users in order to achieve adoption of our recommendations. A project website will be established to facilitate communication of findings and dialogue with key stakeholders. The research will be published in high impact, open access, Journals (e.g. the Lancet, Lancet Child and Adolescent Health, BMJ). Findings will be presented at national and international conferences in the field of Gender Identity Development (e.g. WPATH, EPATH, BAGIS) and Child and Adolescent Health (e.g. ACAMH, RCPH, British Association of Community Child Health, European Society for Paediatric Endocrinology, World International Meeting of Pediatric Endocrinology).

Relevant findings will be communicated and discussed with key external stakeholders including NHS service commissioners, Adult Gender Identity Health Services, CAMHS, primary care, schools and education departments. NHS treatment protocols and guidance will be informed and updated with the findings from this research so that the NHS, service commissioners and clinicians will be better informed with regard to improving both service delivery and individualised care for children and young people and their families.

4 THEORETICAL FRAMEWORK FOR THE QUALITATIVE STUDY

There is a paucity of previous research in this area to guide the selection of a specific theory of childhood gender identity variance to inform the qualitative analysis. Moreover, in keeping with our inductive approach, it is important that the products of the analysis arise from the data and are not imposed on it, and so selecting a specific theory would be premature at this stage. Nevertheless, we are aware of the importance of theory in qualitative analysis, and over the course of the qualitative study we will identify and explore theory that could illuminate the analysis (14).

The method of analysis will be pluralistic. This avoids the pitfalls of constraining the analyses to a specific 'brand' or framework of qualitative analysis and reflects recent recommendations for qualitative researchers to innovate and adjust their methods as appropriate to their data and research goals to achieve 'fidelity' to the data and 'utility' for the particular research questions (15, 16). Others have argued that combining two or more analytical frameworks can produce richer understandings that better reflect the complexity of human experience than drawing on a single framework (17).

5 STUDY DESIGN

This is a prospective cohort study employing a mixed-methods design. It will include children and young people aged 3-13 years at the time their referral was accepted by the UK'S GID service, and their families. It will consist of both quantitative assessments and qualitative interviews at baseline and two further yearly follow-up time points. Please see the attached Gantt chart (Appendix 2) for a detailed timeline of the study.

6 METHODS of DATA COLLECTION

a) Quantitative study

Assessments will be facilitated by two Research Assistants (with supervision and assistance from a Research Coordinator) based at the Tavistock Clinic in London. Assessments will be carried out and recorded online using 'Red Pill', a GDPR-compliant, encrypted online database co-constructed with UCL's PRIMENT Clinical Trials Unit. Participants undertaking online assessments will be assisted either by telephone or via videocall using 'Telemedicine', a secure technology platform similar to 'Zoom' or 'Skype' that allows the researchers to assist, speak to and see participants, dependent on families' preferences and access to technology. In a minority of cases, in case of technical difficulties or participants' preference, we may carry out assessments on site or at a place of the participant's choosing. As the quantitative arm of the study aims to collect data from 638 participants at three timepoints, it will not be possible to collect data from all participants in person within the study's timeframe. For this reason, we are opting to give participants a choice in how to be complete the assessments.

Assessments will include measures of: gender dysphoria and gender identity; social transition status; mental health and psychological wellbeing; Autism Spectrum Disorder traits; self-evaluation of puberty stage, height and weight; cognitive development; quality of life; peer and family relationships; socio-cultural and demographic factors; and health care and societal costs. For a sub-set of participants who will be referred and seen at endocrine clinics, we will request access to data that is routinely collected form those clinical services. As per current NHS treatment protocols, those receiving physical treatment with hormone blockers (GnRH agonists) and/or cross-sex hormones, will be monitored for changes in blood count, renal and liver function, skeletal maturity and bone density and Tanner pubertal staging. Capturing this data will allow adult height predictions to be tracked, and

clinical measurements of body proportions, height, spinal height, shoulder and hip widths and body composition by bioelectrical impedance.

Please see Appendix 3 for a table of all proposed measures.

b) Qualitative study

The qualitative study will involve semi-structured, topic-guided interviews with a purposively sampled sub-set of children and young people from the quantitative study and their parents. We anticipate that the qualitative research associate employed on the LOGIC study will conduct most of the interviews, although where logistical issues arise, other suitably experienced researchers employed on the study may also conduct some interviews. All researchers involved in conducting the qualitative interviews will receive specific training and feedback for this project (see further details of training below) to ensure interviews are developmentally appropriate, conversational in approach and responsive to participants' needs. Interviews will follow the structure of the topic guides attached (Appendix 4), which were developed in collaboration with the peer researcher, wider project team, and the GID service and will be further refined in consultation with external PPI groups. Following good practice in qualitative research, the topic guides will also be developed over the course of the study to explore unanticipated and emerging issues (including over the three interview time points) as informed by ongoing analysis.

We will use a range of resources and strategies to support children and young people interviews, including activities, games, digital technology, creative arts/drawing and toys according to interviewee preference and developmental needs (18). For example, we will use computer assisted interview techniques where these might help to facilitate the engagement of young children, the situationally shy and those with ASD (19, 20). Similarly, we will draw on children and young people's special interests such as video gaming or digital media characters to provide openers for exploring their thoughts about gender, particularly for young people with ASD. Discussions with families at the time of arranging the interviews and before commencing interviews will be used to gauge the needs, preferences and interests of children and young people so we can prepare for and adapt interviews accordingly. This will also include establishing preferred names, pronouns and the particular phrases that children and young people use when referring to gender identity issues, including any changes in these preferences over the course of each participant's three successive interviews.

7. METHODS of DATA ANALYSIS

a) Quantitative study

Statistical analysis will be undertaken by the PRIMENT CTU team who will download the data directly from the Red Pill online database and analyse it using STATA. The characteristics of the children and parents and the outcomes will be presented using mean (SD), median (IQ range) or frequencies (proportion) as appropriate. A logistic regression model will be used to examine the

association between the pre-specified explanatory variables and persistent or ongoing GD. Appropriate regression models will be used to investigate the explanatory variables for the secondary outcomes, physical/endocrine intervention, Mental Health (SDQ), Behavioural and Emotional Functioning (CBCL, YSR) and Quality of Life (Kidscreen 52, CHU-9D). Models will account for the repeated measures of Mental Health and Behavioural and Emotional functioning and quality of life outcomes and the relevant explanatory variables. Exploratory subgroup analyses will be carried out for the prepubertal children and children with autistic traits (as assessed using the AQ) using descriptive statistics and appropriate regression models, where possible. Physical and psychological health outcomes over time will be compared descriptively between those in receipt of hormone blockers (GnRH agonists) and those of a similar age/pubertal stage who progress through puberty without such intervention.

We will report descriptive statistics for health care resource use for children in active contact with GID versus those who are not by a) physical treatment b) social transition c) co-occurring ASD. Published sources will be used to calculate mean total costs for the three groups. Costs will also be reported alongside Quality of Life (Kidscreen 52, CHU-9D), Mental Health (SDQ), and Behavioural and Emotional functioning (CBCL, YSR) as it is not clear what relationship increased costs may have with outcomes for active contact with GID versus not. In particular increased costs related to additional mental health service use will have different implications to increased costs as a result of physical treatment. We will investigate key predictors of costs by including pre specified explanatory variables including "active contact with GID" in appropriate general linear models (GLM). The most appropriate GLM will be chosen using the Akaike information criteria (AIC). This will allow for an estimate of the additional cost or cost-savings associated with active GID contact. Similar models will also be run to test if active contact with GID is related to improvements in Quality of Life. This will be based on quality adjusted life years (QALYs) calculated using the CHU9D, the relevant tariff and the area under the curve. We will run an additional series of GLMs to calculate the net monetary benefit (NMB) of contact with GID services, where for each patient QALYs will be multiplied by a range of values of willingness to pay for a QALY minus the total cost of health and social care services.

Bias due to any missing data in the database and in the cohort study will be investigated. The regression models will be adjusted for predictors of missingness if required and multiple imputation may be used to impute the missing explanatory variables if appropriate. A detailed statistical analysis plan will be prepared nearer the analysis stage.

Should individuals drop out, we will describe and compare the characteristics and outcomes of those who drop-out from the cohort study to those who remain in the study (e.g. demographic characteristics, previous responses, who they are assessed by) to understand whether these have influenced their motivation to leave the study.

All assessment data will be inputted electronically onto the *Red Pill* database system directly. This is a GDPR-compliant, encrypted online database co-constructed with UCL's PRIMENT team. For further information, please see section 10.6.

b) Qualitative study

Analysis of interview transcripts will be inductive, with the key aim of informing health services for children and young people and their families, whilst providing wider contextual insights to understand why, how and for whom service development is needed. Initial analytical questions to be addressed include:

- how gender identity and dysphoria is experienced by participants and how this experience changes over time;
- how a) social transition b) psychological and physical treatment c) a co-occurring diagnosis of ASD is experienced;
- the extent to which assessment processes and physical intervention may reinforce societal 'gender binary stereotypes' or be inadvertently introgenic;
- how participants engage with dilemmas about capacity to provide informed consent to treatment particularly in the context of mental health problems, ASD or varying cognitive and emotional maturity;
- how services and therapeutic protocols can better respond to the needs of children and young people and families;
- what service and treatment outcomes are important to children and young people and their families.

Analysis will be interpretive and pluralistic, drawing on both narrative and thematic approaches (17, 21) and seeking to identify and explore theory that could illuminate interpretations of the data. Both thematic and narrative analytical frameworks have been successfully combined previously (22), including in a previous longitudinal qualitative study of the daily lives, networks and life transitions of children and caregivers (23). Thematic analysis is flexible and accessible and so particularly suited

to our participatory co-production approach and to our aims to inform practice and policy (17). Narrative analysis, which focuses on how participants order, sequence and present their stories and 'turning points' (24) is well suited to the qualitative study's central focus on experiences of changes in gender identity over time and how this links with well-being and experiences of services.

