9.2.2 Sampling technique

a) Quantitative study

All children and young people aged 3-13 years when their referral was accepted by the GID service and awaiting a first appointment will be invited to participate in the study. This includes those currently sitting on the waiting list (n=585) and consecutive new referrals to the service (n~43 p/m) across the 18 month recruitment period. The waiting period will be divided into thirds and research effort equally extended on each third. In this way, we shall strive to treat each interval of waiting equally. Our revised strategy will be reviewed regularly and adapted should there be any change in policy towards, or service throughput of, this age group.

b) Qualitative study

Purposive sampling to the qualitative study will be informed by data from the quantitative study. A key aim is to interview CYP who subsequently go on to experience continuing gender dysphoria and progress to physical treatments, as well as CYP whose gender identity issues subsequently resolve and who do not progress to physical treatments. As these outcomes will not be known at baseline, sampling will take account of factors considered to be associated with these outcomes based on current research evidence and clinical knowledge. To address this we will sample equal numbers of CYP who have socially transitioned at baseline and equal numbers who have not socially transitioned at baseline, although we will review this strategy in the light of new evidence emerging over the course of baseline sampling. Across the whole sample we will aim to interview approximately 12 CYP with co-occurring ASD reflecting the large numbers of such CYP referred to GIDS, and approximately 6-8 black and ethnic minority CYP reflecting the UK general population. Sampling will also aim for balance in family socioeconomic status, location of GIDS and assigned gender at birth. Sampling will also be informed by the ongoing analysis of both the quantitative study data and qualitative data on an iterative basis.

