Appendix 2 – Proposed timeline (please see attached document)

Appendix 3 – Table of procedures and measures

Intervention or procedure	Total no. of interventions or procedures	Average time taken per intervention or procedure	Who will conduct intervention or procedure
Information provision by phone (all appropriate referrals)	1	10 mins	GIDS team member
Information provision by phone (families agreed to be contacted)	1	20 mins	Appropriately trained researcher at Tavistock & Portman
Questionnaire assessment for all parents/carers completed at T0, T1 and T2:	3	40 - 60 mins	Self-report

- Demographics/Background			
(Parent age; Parent gender			
identification; Parent			
employment status; Parent			
education level; Parent			
ethnicity; Parent sexual			
orientation; Child age; Child			
birth assigned sex; Child			
ethnicity; Family living			
situation; Household			
composition; Marital status)			
- Child Gender			
Questionnaire for Parents			
(DSM Criteria for Gender			
Dysphoria; Gender Identity;			
Background to Referral;			
Social Transition; Body			
Image & Distress)			
- Strengths & Difficulties			
· ·			
Questionnaire (SDQ; Brief			
Emotional and Behavioural			
Screener)			
- Child Behaviour Checklist			
(CBCL; Emotional and			
Behavioural Functioning)			
- Autism Quotient 50 item			
scale (AQ; Child (age 4-11) or Adolescent (age 12-15)			
version; Autism Traits)			
- Child and Adolescent			
Service Use Schedule (CA-			
SUS; Health care resource			
use)			
Questions relating to healthcare			
resource use will be adapted by			
[name] (Health Economist)			
, , ,		20 :	
Additional questionnaire assessment	Dependent on	20 mins	Parent proxy report
for parents/carers of children who	age/competence		
are under 12, or refuse to participate but agree to parent/carer	of child at each		
participating, or are lacking capacity	time point (between 0 and		
complete self-report measures at T0,	3)		
T1, or T2:			
- Kidscreen 52 items-			
parental proxy			
(KIDSCREEN-52; Child			
health and well-being)			
U		1	

Identity in Children	1	T	
- Child Health Utility 9			
Dimensions - parental proxy			
(CHU-9D; Quality of life)			
Interview and guided assessment for	Dependent on	60 mins	Self-report
children aged 3-11 years with	age/competence	0 0	and or pro-
capacity to participate at T0, T1, or	of child at each		
T2:	time point		
- Children's Gender Identity	(between 0 and		
Semi-Structured Interview	3)		
- Gender Similarity Task			

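### The protocol promises results for co-occurring autism or ASD, but the only autism measure it lists is the parent-completed AQ trait scale, with no listed diagnosis item and no rule linking AQ scores to the ASD groups

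*Protocol*

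**What the plan says.** The protocol uses three terms for one exposure.

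- **Autism or ASD.** Section 3 asks "What is the impact of a) physical treatment b) social transition c) co-occurring autism on, physical health" and other outcomes, including cost. Section 7a describes resource use for children in active contact with the service "versus those who are not by a) physical treatment b) social transition c) co-occurring ASD". Section 9.2.2b sets an interview target of "approximately 12 CYP with co-occurring ASD reflecting the large numbers of such CYP referred to GIDS".
- **A diagnosis.** Section 7b lists, among its analytical questions, how "c) a co-occurring diagnosis of ASD is experienced".
- **Traits.** Section 6a lists "Autism Spectrum Disorder traits" among the constructs assessed. The exploratory subgroup in section 7a is "children with autistic traits (as assessed using the AQ").

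Appendix 3 lists one autism instrument, the 50-item AQ, in the block completed by all parents or carers at T0, T1 and T2. The itemised demographics list contains no ASD diagnosis. Neither do the headings of the gender questionnaires, the child and youth measures, or the routine data requested for children on endocrine treatment. A second autism-related scale, the SRS-2, appears only in the list of abbreviations.

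**The concern.** A trait score and a clinical diagnosis are different constructs. Some children score high on a trait scale without having ASD, and some diagnosed children are rated low by their parents. If AQ scores stand in for co-occurring ASD, both kinds of error enter the groups, and the reported result answers a different question from 3c.

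This is more than a labelling matter. Co-occurring ASD is presented as a main exposure in the background, rationale and outcome sections. Section 10.4 records that it was the major area of interest among the parents who discussed the draft proposal. The later statistical analysis plan announced in section 7a can set an AQ cut-off, but it cannot supply a baseline diagnosis that was never collected. What is collected is fixed in this document.

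**Working it through.** **1. The plan's own figures.** The protocol gives no sample size, precision or effect size for an ASD contrast. Its general chain reproduces: 0.70 × 912 = 638.4 (stated 638); 638 × 0.80 = 510.4 (stated 510); 510 × 0.40 = 204 (stated 204). None of this is in dispute; only the 510 is used below.

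**2. Is there a link from measure to group?** Section 6a and Appendix 3 supply a trait score. Sections 3 and 7a (costs) require an ASD group. Neither these sections nor any other gives a cut-off, a diagnosis variable or another rule connecting the two.

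**3. Size if misclassification is unrelated to outcome.** Suppose the AQ is cut into two groups. With prevalence π, sensitivity Se and specificity Sp for diagnosis:

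- flagged share f = π·Se + (1 − π)(1 − Sp)
- PPV = π·Se / f; NPV = (1 − π)·Sp / (1 − f)
- observed difference = true difference × (PPV + NPV − 1)

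The documents give none of π, Se or Sp, so all are assumptions.

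| Se / Sp | π = 10% | π = 20% | π = 30% |
|---|---|---|---|
| 0.95 / 0.95 | 0.67 | 0.81 | 0.87 |
| 0.90 / 0.90 | 0.49 | 0.67 | 0.75 |
| 0.80 / 0.80 | 0.28 | 0.44 | 0.54 |

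Worked cell (π = 30%, 0.80/0.80): f = 0.24 + 0.14 = 0.38; PPV = 0.24/0.38 = 0.632; NPV = 0.56/0.62 = 0.903; factor = 0.535.

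The table runs from 0.28 to 0.87. These are not bounds: at 0.70/0.70 the factor is 0.16 to 0.35 over the same prevalences.

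For an assumed true difference of 0.4 SD, with 510 children and π = 30%, power falls from 98.5% with correct classification to 89% (0.90/0.90) or 65% (0.80/0.80).

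**4. What changes if the same parent rates both.** Appendix 3 has the parent complete the AQ, SDQ, CBCL and service-use schedule. A simulation of 2,000,000 records used π = 30%, a true difference of 0.40 SD, and a parental rating tendency with loading 0.5 on the outcome and a varying loading on the trait score. Sensitivity and specificity stayed at about 0.84 throughout.

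| Loading on trait score | Trait-group difference | Ratio to true (0.402 realised) |
|---|---|---|
| 0 | 0.25 | 0.62 |
| 0.3 | 0.41 | 1.01 |
| 0.6 | 0.57 | 1.41 |

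The same accuracy therefore gives a diluted, unchanged or inflated contrast, depending on shared rating error that the documents do not quantify.

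**The case against.** Several points on the other side are fair.

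- **Absence of a diagnosis item is not proven.** A reader might infer that no diagnosis is collected at all. Appendix 3 gives instrument names and short content headings, not items. The content of Background to Referral and of the CA-SUS is not shown, and the resource-use questions are still to be adapted. The documents support only that no diagnosis item is listed.
- **Dilution is not established.** A reader might infer that the ASD contrast must shrink towards zero. That requires error unrelated to outcome, and step 4 shows why a shared rater makes this doubtful.
- **The numbers have little anchor.** Accuracy figures are not in the protocol. The 30% implied by 12 of 40 is a purposive interview target, not a cohort prevalence. The formula also assumes a dichotomised AQ, whereas the score could be used whole.
- **The subgroup wording is sound in itself.** It names both construct and instrument, and the analysis is exploratory. The conflict is with research question 3c, the cost groups and the reference to a diagnosis. The resource-use breakdown is descriptive, and no sample size rests on it.
- **The interviews are largely safe.** Section 9.2.2b says "Purposive sampling to the qualitative study will be informed by data from the quantitative study", but does not restrict sampling to those data. Section 6b provides for discussions with families when interviews are arranged, and a diagnosis can be reported then. The question in section 7b can be answered from the family's account.
- **Diagnosis is imperfect too.** It depends on access to assessment.

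These points limit the claim about size and direction. They do not remove the mismatch between the exposure named in question 3c and the cost groups and the measure listed for it.

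**Conclusion.** The concern holds in a limited form. The protocol commits to results on co-occurring autism or ASD, lists only a parent-rated trait scale, and gives no rule joining the two. Unless an unlisted diagnosis item exists, results headed co-occurring ASD would be about parent-rated traits.

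The numerical effect cannot be stated from the documents. About 0.3 to 0.9 of the true difference is an illustration, conditional on a dichotomised AQ, prevalence of 10% to 30%, sensitivity and specificity both between 0.80 and 0.95, and error unrelated to outcome. With shared-rater error, the illustrative ratio runs from 0.62 to 1.41. The conclusion rests on the mismatch of construct, not on any of these figures. The affected contrasts are descriptive or exploratory, but they answer a named research question, so the change should be made.

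**What to change.** Add one item to the parent background questionnaire at T0, T1 and T2: formal ASD diagnosis (yes / on assessment pathway / no). If such an item already exists, name it in section 6a and Appendix 3. Use diagnosis at T0 to define co-occurring ASD in research question 3c and in the resource-use and cost groups of section 7a. Analyse the AQ separately, and label those results autistic traits.

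If no diagnosis item is added, reword research question 3c, the groups in section 7a and the quota in section 9.2.2b as autistic traits, with a stated AQ rule.

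The cost is one extra parent item and a protocol amendment, with ethics review if it is judged substantial. Checking answers against referral records would need new data access and is not required. The remaining weakness is that undiagnosed autistic children stay in the comparison group; keeping the AQ as a second measure helps to show how far this matters.
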